## Statistical Analysis Plan

The data were analysed using the Statistical Package for the Social Sciences (SPSS) version 26.0. The normality of distribution for the numerical variables related to the patients and the evaluated interdental papilla sites was assessed based on skewness and kurtosis values. Normality of continuous data will be assessed using the Shapiro–Wilk test and visual inspection of Q–Q plots. A reference range of  $\pm 1.96$  was adopted as the criterion for normal distribution (Kalayci, 2005).

For each material, changes over time from baseline to follow-up will be analysed using repeated-measures ANOVA when assumptions are met, or the Friedman test in the case of non-parametric or ordinal data. Post-hoc pairwise comparisons between time points will include Bonferroni adjustments. Since the study design is split-mouth, inter-group comparisons between HA and i-PRF at each time point, as well as comparisons of change scores, will use paired t-tests for normally distributed variables and Wilcoxon signed-rank tests otherwise. PPI, being ordinal, will be evaluated with non-parametric paired procedures. Subgroup analyses will be performed separately for maxillary and mandibular papillae using similar paired or repeated-measures methods. Patient-reported VAS outcomes will be analysed using repeated-measures methods for within-group changes and paired testing for between-group differences.

Comparisons of KTT and IBC-ICP measurements across jaw localizations and treatment groups, as well as intergroup analyses of clinical outcome variables, were performed using the One-Way ANOVA test. Intragroup comparisons of variables measured at different time points were conducted using the Repeated Measures ANOVA. Where applicable, Post Hoc tests were employed to further investigate significant intergroup differences.

Additionally, to evaluate the relationship between KTT and IBC-ICP measurements and the percentage changes in clinical parameters, the Spearman correlation test was used. In interpreting the correlation coefficients, a range of 0.00–0.30 was considered low, 0.30–0.70 moderate, and 0.70–1.00 high. A significance level of  $p < 0.05$  and  $p < 0.01$  was adopted for all statistical analyses.

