## Study design

This randomized split-mouth clinical trial included 13 systemically healthy adults with a total of 65 papilla deficiencies in the aesthetic zone. The study was approved by the Altınbaş University Ethics Committee. All participants provided written informed consent.

Inclusion criteria required  $\geq 2$  papillae classified as Papilla Presence Index (PPI) class 2 or 3, probing depths  $\leq 3$  mm, and plaque and bleeding scores below 15%. Exclusion criteria included PPI class 4, diastema, active periodontal disease, smoking, pregnancy, systemic conditions influencing healing, anticoagulant use, and previous surgical papilla reconstruction.

For each participant, one side was randomly assigned HA and the contralateral side i-PRF. The clinical examiner underwent intra-examiner calibration until repeated measurements were consistent within  $\pm 1$  mm. Outcome assessments were performed by a blinded examiner.

For i-PRF sites, 10–20 mL of venous blood was collected into plastic tubes and centrifuged at 700 rpm for 3 minutes. The upper orange plasma layer was aspirated and transferred to 1-mL insulin syringes. Injections were delivered within 5 minutes to ensure liquid consistency before polymerization.

All treatments were performed with buccal infiltration anesthesia. HA or i-PRF (0.1–0.2 mL) was injected from the buccal aspect, 2–3 mm apical to the papilla tip, at a 45° angle. A single

puncture per session was used to minimize trauma. Slight blanching indicated correct placement. Each papilla received three injections at baseline, week 3, and week 6.

Participants avoided mechanical oral hygiene for 24 hours and interdental brushes for one week, replacing them with 0.12% chlorhexidine rinses. Modified Bass brushing resumed the following day.

Standardized photographs were obtained using a custom photograph standardization device (PSD), enabling consistent image acquisition. Black triangle height (BTH), width (BTW), area (BTA), and papilla height (PH) were measured at baseline, 1 month, and 3 months using ImageJ. PPI was recorded visually. Radiographs were taken to measure the distance between the interdental bone crest and contact point (IBC-ICP). Keratinized tissue thickness (KTT) was measured at baseline.

Pain was assessed after each injection using a VAS scale from 0 (none) to 10 (worst). Aesthetic satisfaction was rated at each visit using a VAS scale from 0 (not satisfied) to 10 (highly satisfied).

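### The SAP does not say how several papillae per participant and side enter the tests; run on papillae, the within-material tests would reject too often

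*Combined protocol and SAP*

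**What the plan says.** The Study design section reports "13 systemically healthy adults with a total of 65 papilla deficiencies in the aesthetic zone". Treatment is allocated by side: "For each participant, one side was randomly assigned HA and the contralateral side i-PRF". Entry requires at least two "papillae classified as Papilla Presence Index (PPI) class 2 or 3"; the number per participant or per side is not reported.

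The second paragraph of the Statistical Analysis Plan gives the within-material analysis: "For each material, changes over time from baseline to follow-up will be analysed using repeated-measures ANOVA when assumptions are met", otherwise Friedman, with Bonferroni-adjusted pairwise comparisons of visits. For HA versus i-PRF the same paragraph names paired t-tests or Wilcoxon signed-rank tests and justifies the pairing by the split-mouth design.

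The SAP does not define the unit of analysis or what makes up a pair. It mentions no averaging to side or participant, and no mixed model, GEE or cluster-robust error. Its clues point to papillae as rows. The normality check covers "numerical variables related to the patients and the evaluated interdental papilla sites", subgroups are defined by maxillary and mandibular papillae, and the bone-crest-to-contact distance, which is a site measurement, is correlated with percentage changes in the clinical parameters.

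**The concern.** Repeated-measures ANOVA, Friedman, the paired t-test and the Wilcoxon signed-rank test all assume that the rows are independent of one another. Papillae on one side of one mouth share the host, the oral hygiene, the treatment session and, on i-PRF sides, plausibly the same blood draw. Their changes are therefore likely to be correlated.

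Repeated-measures ANOVA on papillae removes each papilla's own level, but not a response to treatment that is common to a participant's papillae. That common response then counts two or three times as if it were separate evidence. The background section hypothesises significant improvement with both materials, so this test carries half of the stated hypothesis. The comparison of materials is exposed differently, because pairing removes part of the clustering.

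**Working it through.** The plan gives no sample-size, SD or correlation figure, so there is no stated number to reproduce. Everything below that depends on a correlation or a layout is an assumption.

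**Inputs from Study design.** 13 participants, 65 papillae, side randomised within participant.
- Papillae per participant: 65/13 = 5.0.
- Sides: 2 x 13 = 26. Papillae per side: 65/26 = 2.5.
- Papillae per material: 65/2 = 32.5, that is 32 or 33.

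**Step 1: approximate inflation of the within-material variance.** Design effect = 1 + (m - 1) x ICC, with m = 2.5.

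| Assumed ICC | Design effect | True SE / nominal SE (square root) | Effective papillae (32.5 / design effect) |
|---|---|---|---|
| 0.2 | 1 + 1.5 x 0.2 = 1.30 | 1.14 | 25.0 |
| 0.4 | 1 + 1.5 x 0.4 = 1.60 | 1.26 | 20.3 |
| 0.6 | 1 + 1.5 x 0.6 = 1.90 | 1.38 | 17.1 |

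This takes equal numbers per side. Unequal numbers make it worse.

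**Step 2: false-positive rate of the named within-material tests.** Simulation with no true change over three visits, 33 papillae in 13 participants, two-sided 0.05. The correlation is the share of visit-to-visit variation common to a participant's papillae.

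| Test and rows | Layout per side | 0.2 | 0.4 | 0.6 |
|---|---|---|---|---|
| Repeated-measures ANOVA, papillae | even, 2-3 | 10% | 16% | 23% |
| Repeated-measures ANOVA, papillae | uneven, 1-5 | 13% | 21% | 29% |
| Friedman, papillae | even, 2-3 | 8% | 13% | 19% |
| Friedman, papillae | uneven, 1-5 | 10% | 17% | 23% |
| Either test, participant means | both | about 5% | about 5% | about 5% |

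Repeat runs, with other uneven layouts, move these rates by a point or two. At a correlation of 0.1, ANOVA on papillae gives roughly 7% to 9%.

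**Step 3: HA versus i-PRF.** Write a papilla's change as a participant effect common to both sides, plus a participant-by-side effect, plus papilla error. In an HA minus i-PRF difference the common effect cancels, and only the participant-by-side effect leaves differences from the same person correlated. Simulated type I error of a paired t-test on papilla pairs, at nominal 0.05:
- all clustering common to both sides: 0.046-0.052;
- participant-by-side variance at 0.1-0.5 of the total: 0.063-0.110 (even layout), 0.081-0.191 (uneven);
- 13 paired differences of side means: 0.044-0.053 throughout.

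**Step 4: can papillae be paired at all?** 65 is odd, so at least one papilla has no one-to-one partner on the other side. The SAP gives no matching rule.

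**The case against.** The strongest reply is that the plan does recognise the participant. It uses paired tests because the design is split-mouth, which links the two sides of one person. If each pair is a participant's two side means, those tests are valid with n = 13. That stands. The gap is that the pair is not defined.

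A second reply is that papillae as rows is an inference. The normality sentence also mentions patient-level variables, and a subgroup label does not fix the analysis row. This also stands in part: the text permits papilla-level rows and leans that way, but does not prescribe them. Patient-reported VAS scores may be recorded per person or per side and are not shown to be affected. If averaging was intended, the SAP needs to say so, because nothing printed in it leads an analyst to 13 values.

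A third reply concerns direction. For HA versus i-PRF, clustering does not always make errors too small. A participant effect common to both sides cancels in paired differences. It even makes the one-way ANOVA named in the third SAP paragraph conservative (type I error 0.041 / 0.026 / 0.013 at shared shares of 0.1 / 0.3 / 0.5, even layout). This stands for the comparison of materials. It does not help the within-material tests, where nothing cancels.

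**Conclusion.** The omission is certain, and it matters most for within-material improvement. If papillae are the rows, the false-positive rate there exceeds 5% for any positive correlation: about 10% to 29% for repeated-measures ANOVA and 8% to 23% for Friedman over assumed correlations of 0.2 to 0.6 and the two assumed layouts. At a correlation of 0.1 the excess is modest. The documents supply neither the correlation nor the layout, so these are ranges and not estimates for this trial.

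A reader might go further and infer that all the named tests ignore the participant, that 65 papillae enter each test, and that the HA versus i-PRF standard errors are necessarily too small. The documents do not support that. The paired tests tie the sides together within a person, and each within-material test uses about 33 papillae. Inflation for the material comparison needs participant-by-side clustering. Such clustering is plausible, since side is the randomised unit, but its size is unknown.

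Because a stated hypothesis rests on the within-material tests, the unit of analysis should be settled before their p-values are relied on.

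**What to change.** State in the SAP that the participant is the unit of inference. At each visit, average the papillae within participant and side, and run repeated-measures ANOVA, Friedman, the paired t-test and Wilcoxon on those means (n = 13 per material, or 13 pairs). For the jaw subgroups, average within jaw as well, and state how many participants contribute. For PPI, state the side-level summary of this ordinal score in advance. Report the number of papillae per participant and side. Entry requires at least two papillae but does not expressly require one on each side, so also say what happens if a side has none.

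A papilla-level mixed model with random effects for participant, participant-by-side and papilla, and small-sample degrees of freedom, can serve as a supporting analysis. It should not be the main one, because with 13 participants the variance estimates may be unstable or fall to zero.

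The cost is SAP wording and a re-run on data already collected. Intervals will generally be wider and p-values larger, and each participant will count equally whatever the number of papillae contributed.

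### The planned repeated-measures ANOVA and Friedman tests use only records complete at all three visits, so one missed visit discards recorded values and the within-material gains describe completers only

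*Combined protocol and SAP*

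**What the plan says.** Under Study design, "This randomized split-mouth clinical trial included 13 systemically healthy adults with a total of 65 papilla deficiencies in the aesthetic zone". Sides are randomised within patients: "For each participant, one side was randomly assigned HA and the contralateral side i-PRF". The photographic outcomes (BTH, BTW, BTA and PH) "were measured at baseline, 1 month, and 3 months using ImageJ", and the treatment course has three sessions: "Each papilla received three injections at baseline, week 3, and week 6".

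In the second paragraph of the Statistical Analysis Plan, the within-material rule is that "changes over time from baseline to follow-up will be analysed using repeated-measures ANOVA when assumptions are met, or the Friedman test". HA and i-PRF are compared by paired t-tests or Wilcoxon signed-rank tests, at each time point and on change scores. The third paragraph names Repeated Measures ANOVA again for intragroup comparisons and One-Way ANOVA for intergroup comparisons of clinical outcomes. For the patient-reported scales, "Patient-reported VAS outcomes will be analysed using repeated-measures methods for within-group changes and paired testing for between-group differences".

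No section defines an analysis population, a rule for missed visits or withdrawals, imputation, a mixed model or a missing-data sensitivity analysis. No section states how many patients were assessed at 1 and 3 months.

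**The concern.** The problem comes from the methods named, not only from the absence of a missing-data section. Classical repeated-measures ANOVA and the Friedman test work on rows that are complete across visits. A patient seen at baseline and 3 months but not at 1 month drops out of the within-material analysis, although both ends of the baseline-to-3-month change were measured. A patient seen at baseline and 1 month but not at 3 months loses those two values as well.

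The Scientific Background hypothesises significant improvement with both materials and no clinically meaningful difference between them. The within-material analysis tests the improvement half directly, and it is the analysis that deletes whole records. If patients with a poor early result are more likely not to return, the gains shown for both materials are too large. The within-material gains and the paired comparisons could also rest on different patients. With 13 patients, each deletion is 1/13 = 7.7% of the sample and on average 65/13 = 5 papillae.

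**Working it through.** The plan gives no sample-size calculation, standard deviation, dropout rate or missing-data figure, so there is none to reproduce. From Study design: 13 patients, 65 papillae (5 per patient, 2.5 per side) and three outcome visits. Every missing-data rate below is an assumption.

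**1. Behaviour of the named tests.** In simulated data for 13 patients and 3 visits, one 1-month value was removed, leaving 13 × 3 − 1 = 38 values. The repeated-measures ANOVA routine used (in Python, not SPSS) rejected the data as unbalanced, and the Friedman routine returned no result. Both can be run only on the 12 complete records, which discards 2 recorded values. A paired contrast behaves differently: baseline to 1 month keeps 12 patients, and baseline to 3 months keeps all 13.

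**2. Records lost.** Let q be the assumed chance of missing each follow-up visit, independently. Expected complete records are 13(1 − q)² for repeated-measures ANOVA or Friedman, and 13(1 − q) for a paired test at one visit when both sides of a patient are missed together.

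| q | ANOVA or Friedman | Paired test at one visit | Share dropped by the three-visit rule, 1 − (1 − q)² |
|---|---|---|---|
| 5% | 11.7 | 12.35 | 9.8% |
| 10% | 10.5 | 11.7 | 19.0% |
| 15% | 9.4 | 11.05 | 27.8% |
| 20% | 8.3 | 10.4 | 36.0% |

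**3. Bias in the mean gain.** Assume gains with SD 1, means of 0.6 at 1 month and 1.00 at 3 months, and correlation 0.7. Loss before 3 months follows a logistic model in the 1-month gain, with overall loss held at 16% (0.16 × 13, about 2 patients). The slope is the fall in log-odds of loss per SD of better 1-month gain. The last column regresses the 3-month gain on the 1-month gain in completers and averages the prediction over everyone seen at 1 month. This is the information that a likelihood-based model adds.

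| Slope | Completer mean | Using recorded 1-month values |
|---|---|---|
| 0 | 1.00 | 1.00 |
| 0.5 | 1.05 | 1.00 |
| 1.0 | 1.10 | 1.00 |
| 1.5 | 1.13 | 1.00 |
| 2.0 | 1.15 | 1.00 |

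A second simulation with correlation 0.8 and a true 3-month gain of 0.99 gave completer means of 1.08 to 1.29 at 14% to 30% selective loss. With loss unrelated to the 1-month gain, the completer mean was 0.99. The estimate using 1-month values stayed at 0.99 throughout. The direction is stable; the size depends on the assumptions.

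**4. What no such model recovers.** Suppose k of 13 patients leave before 1 month with no gain, and completers gain 1.00 on average. The all-patient gain is (13 − k)/13: 0.92, 0.85 and 0.77 for k = 1, 2, 3. The completer mean therefore overstates it by 13/(13 − k) − 1 = 8%, 18% and 30%. With baseline values only, and baseline unrelated to gain, the likelihood estimate is also 1.00. These percentages describe a risk that the fix does not remove.

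**5. The variance structure that the fix needs.** Sides are the randomised units. Change scores were simulated with no true difference, and the analysis model had no side (participant-by-material) effect. For assumed side-level shares of within-patient variance of 10%, 20% and 30%, the false-positive rate was about 7%, 10% and 13% at nominal 5%, against about 5–6% for a patient-level paired test.

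**The case against.** The strongest objection is that nothing may have been lost. Study design is written in the past tense: patients were included, injections were received and outcomes were measured. No withdrawal or missed visit is mentioned, and with full attendance the named tests discard nothing. This stands and makes the point conditional. It does not dispose of it: the wording describes procedures rather than attendance at 1 and 3 months, and much of the analysis plan is still in the future tense.

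A reader might infer four stronger things that the documents do not support.

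- That every named method needs a complete record. The paired tests need only the pair for the contrast tested, so a missed 1-month visit leaves the 3-month comparison intact. The One-Way ANOVA in the third paragraph would keep an unpaired side; its conflict with the paired tests is a separate matter.
- That i-PRF sides would be lost selectively because of the blood draw, the centrifugation and the time limit ("Injections were delivered within 5 minutes to ensure liquid consistency before polymerization"). A failed preparation prevents an injection, not a photograph. Both sides belong to one patient, so a missed visit normally removes both, and the plan does not exclude an under-injected side.
- That pain scores suffer most. The VAS sentence refers only to repeated-measures methods, which a mixed model satisfies. Paired testing after the first session loses nobody through later stopping. There is no case here for making the first-session score the main pain comparison.
- That the 8%, 18% and 30% overstatements are what a mixed model would repair. Step 4 shows that they are not. In step 3, loss was generated from recorded values, so the model's assumption holds by construction.

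**Conclusion.** The point holds in a limited form and is worth correcting. The within-material analyses in the second paragraph of the Statistical Analysis Plan would use only records complete at all three visits. Any patient with one missed visit would lose recorded values, and the before-after gains would describe completers.

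Under an assumed 16% loss before 3 months that follows the 1-month result, the completer gain is overstated by about 5% to 15%, depending on how strongly loss follows that result. The overstatement is nil if loss is unrelated to the gain, and nothing is lost if all 13 patients attended every visit. The documents do not show which case applies. The point concerns the within-material gains; for the paired tests, a missing value affects only its own contrast.

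**What to change.** For BTH, BTW, BTA and PH, replace the separate per-material repeated-measures ANOVAs with one linear mixed model (MIXED in SPSS, the software already named), fitted to every recorded value:

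- fixed effects for material, visit and material-by-visit;
- random effects for participant, side within participant (participant-by-material) and papilla within side;
- a small-sample degrees-of-freedom correction.

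The side effect must not be left out, for the reason in step 5; a degrees-of-freedom correction does not replace a missing variance component. Both materials' gains and their difference then come from one model and one set of patients.

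State that each side is analysed under its assigned material regardless of the number of injections received. Report the numbers analysed per material and visit. Keep the planned repeated-measures, Friedman and paired tests as complete-record sensitivity analyses. PPI is ordinal and stays with its planned non-parametric procedures, so for PPI the reported numbers are the safeguard.

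The cost is SAP wording and one model, with no added visits or measurements. There are two downsides. Variance components are imprecise with 13 patients. The model also assumes that missingness depends only on recorded values, and it cannot recover patients with baseline data only.

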# Study Protocol with Statistical Analysis Plan

## Scientific Background

Loss of the interdental papilla is a frequent aesthetic concern, particularly in the anterior region where even minor deficiencies create visible black triangles. These deficiencies contribute to plaque accumulation, food impaction, and phonetic disturbances, in addition to compromising smile harmony. Earlier attempts to reconstruct missing papillae through surgery often yielded unpredictable outcomes, largely due to the delicate blood supply of the papillary region. As a result, attention has shifted toward non-surgical injectable biomaterials designed to restore soft-tissue volume with minimal invasiveness.

Hyaluronic acid (HA) dermal fillers have become widely used in aesthetic and periodontal therapy due to their biocompatibility, hydrophilicity, and ability to stimulate wound healing. Clinical studies have consistently reported partial or complete closure of black triangles following repeated HA injections. Injectable platelet-rich fibrin (i-PRF), prepared via low-speed centrifugation, represents an autologous alternative that provides a fibrin scaffold enriched in platelets and leukocytes. Its gradual release of growth factors promotes angiogenesis, fibroblast proliferation, and extracellular matrix formation.

Despite increasing interest, direct comparisons between these two materials are scarce, and previous trials have not used a split-mouth design to minimize interpatient variability. This study directly compares HA and i-PRF administered under identical intraoral conditions. We hypothesized that both would yield significant improvement in papilla fill without clinically meaningful differences between them.

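### The HA versus i-PRF comparison of BTH, BTW, BTA and PH uses raw values and change scores, with no baseline covariate and no named main result; one baseline-adjusted analysis would be a cheap improvement

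*Combined protocol and SAP*

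**What the plan says.** Under Study design, the four image-based measures (BTH, BTW, BTA, PH) "were measured at baseline, 1 month, and 3 months using ImageJ". Allocation is within patient: "For each participant, one side was randomly assigned HA and the contralateral side i-PRF". There are 13 participants with 65 papillae, and eligibility covers "papillae classified as Papilla Presence Index (PPI) class 2 or 3".

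The second paragraph of the Statistical Analysis Plan states that "inter-group comparisons between HA and i-PRF at each time point, as well as comparisons of change scores, will use paired t-tests" when data are normal, with the Wilcoxon signed-rank test otherwise. The third paragraph says that "intergroup analyses of clinical outcome variables, were performed using the One-Way ANOVA test". Neither paragraph names a baseline covariate. Nothing in the document says whether the raw or the change-score comparison is the main one. The Bonferroni adjustment covers only comparisons between time points.

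The hypothesis in Scientific Background is that both materials improve papilla fill "without clinically meaningful differences between them".

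**The concern.** Each outcome at each follow-up has two answers to the same question, and no rule says which one counts. The two differ only in how they treat baseline: the raw comparison ignores it, and the change score subtracts it in full. If the true slope lies between these extremes, each is less precise than it could be, and each is pulled in a different direction by a chance baseline difference between sides.

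Such a difference is plausible. Papillae of two PPI classes are eligible, there are at most 13 patient pairs, and 65 is an odd number, so the papillae cannot all match one-to-one across sides. It also bears on the hypothesis: a claim of no meaningful difference rests on one clear estimate and the width of its confidence interval, not on a set of non-significant p-values.

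**Working it through.** The plan gives no SD, correlation, power or sample-size figure, so there is nothing of its own to reproduce.

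**Inputs.** From Study design: 13 participants, side randomised, baseline measured. Assumed: one mean per side per patient, 13 usable pairs (10 as a variant), normal data, equal SDs of the HA minus i-PRF difference at baseline and follow-up, two-sided 0.05, and r = 0.3, 0.5 or 0.7, where r is the correlation between the baseline and follow-up side differences. The unit is the SD of the paired difference.

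**1. Effect of a chance imbalance.** Let d be the mean baseline difference between sides and b the slope of the follow-up difference on the baseline difference. Given d, the raw comparison is off by b·d and the change score by (b − 1)·d. The adjusted estimate is not off if the relation is linear. With equal SDs b = r, so at b = 0.5 and d = 0.5 SD the errors are +0.25 and −0.25 SD.

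**2. Variance relative to raw.** Raw is 1, change is 2(1 − r), and adjusted is (1 − r²)(1 + 1/(n − 3)). The last factor is 1.10 at n = 13 and 1.143 at n = 10.

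| r | Change | Adjusted, n = 13 | Adjusted / better planned test, n = 13 | Same ratio, n = 10 |
|---|---|---|---|---|
| 0.3 | 1.40 | 0.91 × 1.10 = 1.001 | 1.001 (raw) | 1.040 |
| 0.5 | 1.00 | 0.75 × 1.10 = 0.825 | 0.825 (either) | 0.857 |
| 0.7 | 0.60 | 0.51 × 1.10 = 0.561 | 0.561/0.60 = 0.935 (change) | 0.971 |

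Writing f for that factor, adjusted equals raw at r = √(1 − 1/f) and equals change at r = 2/f − 1. These limits are 0.302 and 0.818 at n = 13, and 0.354 and 0.750 at n = 10. Outside them adjustment loses a little at n = 13: 10% in variance against raw at r = 0, and (1.9 × 1.10)/2 = 1.045, or 4.5%, against change at r = 0.9.

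**3. Simulation, 13 pairs, 200,000 trials per setting** (order: raw / change / adjusted).

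| r | Mean 95% CI half-width (SD) | Power at 0.8 SD (%) |
|---|---|---|
| 0.3 | 0.592 / 0.700 / 0.595 | 75 / 61 / 75 |
| 0.5 | 0.592 / 0.592 / 0.541 | 75 / 75 / 82 |
| 0.7 | 0.592 / 0.459 / 0.446 | 75 / 93 / 94 |

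**4. Type I error.** Averaged over randomisations, all three tests are at 4.9–5.1%. Given the imbalance, the planned tests depart from this:

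| Imbalance d (SD) | Raw, r = 0.3/0.5/0.7 (%) | Change, r = 0.3/0.5/0.7 (%) |
|---|---|---|
| 0.19 (median: 0.6745/√13) | 4.5 / 3.6 / 2.4 | 3.2 / 3.7 / 4.2 |
| 0.28 | 5.0 / 4.9 / 4.4 | 4.8 / 4.9 / 5.0 |
| 0.5 | 7.0 / 10.2 / 14.9 | 12.2 / 10.3 / 8.2 |

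The adjusted test stays at 4.9–5.1% throughout. An imbalance above 0.5 SD has probability 2Φ(−0.5√13) = 0.071.

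**5. Two tests with no main one.** Under the null, at least one of raw and change has p < 0.05 in 8.9, 9.2 and 9.4% of trials at r = 0.3, 0.5 and 0.7, per outcome and follow-up. Contradictory signs with either test significant are rare, at 0.7, 1.1 and 1.9%.

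**The case against.** The strongest reply is that this is a preference. The planned change score already adjusts for baseline, side is randomised, and each test holds its 5% level on average. That stands, and it is why the point is an improvement and not an error.

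The gain also depends on an r that nobody has stated. Against the better planned test, the half-width at 13 pairs is unchanged at r = 0.3, about 9% narrower at r = 0.5 and 3% narrower at r = 0.7. With 10 pairs it is slightly worse at r = 0.3 (0.717 against 0.696) and level at r = 0.7. With 6 pairs adjustment is worse at all three values. Eligibility asks for at least two papillae per patient, not one on each side, so the number of usable pairs is unknown. All this stands. But the better planned test is not known in advance either, and adjustment protects against having chosen the worse one.

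It is fair, too, that the 0.5 SD imbalance is a tail case, and that the 9% figure comes from not naming a main test: naming either planned test would restore 5%. The figures describe patient-level paired t-tests. They do not describe Wilcoxon tests, papilla-level tests or the unpaired One-Way ANOVA in the third paragraph. That paragraph conflicts with the paired tests and must be reconciled in its own right, but it offers no baseline adjustment.

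Last, parts of the plan are in the past tense ("The data were analysed using the Statistical Package for the Social Sciences (SPSS) version 26.0"), so a new main analysis may be post hoc. So would any main test named now. The answer is to label it, and not to add it as a third unranked option: if any of the three tests could be cited, the null error would be about 9–10%.

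**Conclusion.** The point holds as a worthwhile change, with medium confidence. The plan tests raw values and change scores, adjusts for no baseline value and names no main result. Under the stated assumptions, one adjusted analysis with 13 pairs matches or improves on the better planned test for r between about 0.30 and 0.82, with its largest gain near r = 0.5 (17.5% in variance). It also holds its 5% level whatever the baseline imbalance. The precision gain rests on r, equal SDs and the number of usable pairs, none of which the documents give. The benefit that does not depend on r is having one named test instead of two. Adjustment alone does not establish that there is no clinically meaningful difference, since the plan states no margin.

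**What to change.** For BTH, BTW, BTA and PH, name one baseline-adjusted within-patient analysis as the main HA versus i-PRF comparison:

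- Average the papillae on each side, in each patient with papillae on both sides.
- Regress the HA minus i-PRF follow-up difference on the HA minus i-PRF baseline difference.
- Report the intercept, its 95% CI and the number of patients used.
- Keep the raw-value and change-score tests as supportive only.
- Label the adjusted analysis post hoc if outcomes have already been seen.
- Optionally, if residuals are clearly non-normal, use a randomisation test of the same intercept over the possible side assignments.

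This keeps the pairing and does not treat 65 papillae as independent. It does not settle which outcome and follow-up time is primary; the plan must state that separately.

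The cost is SAP wording, the averaging step and one covariate, with no new data. One residual degree of freedom is lost (critical t goes from 2.18 to 2.20 at 13 pairs), with a small loss of precision if r falls outside the limits above or usable pairs are few.
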